8.6.2.4.2 Rate Ratio of Clinically Meaningful Changes by Baseline Tau Scan Status

The analyses for clinically meaningful changes will be restricted to AD/MCI subjects only.

Clinically meaningful changes assessed by psychometric scores are defined in section 6.4.2.3.1

For each of the categorized clinically meaningful changes (event) except for CDR global score change, a Poisson regression model will be applied. The model will have these defined event as dependent variable respectively, and the independent variables will include tau status at baseline (AD++ vs. non-AD++), visit and the interaction of tau status and visit as a categorical variable, and continuous covariates that include baseline psychometric score, age, and ANART.

At each visit, person-year will be calculated for each subjects, as time from baseline to first event, or time from baseline to visit date or end of study if no event for the subject.

General estimating equation (GEE) technique will be used to adjust for the intra subject correlation. The variance-covariance matrix is pre-specified: each model should be fit using the unstructured covariance structure. If this structure does not converge, the exchangeable, auto-regressive, and m-dependent structures will be fit and the model with the lowest BIC value will be selected to use. The rate ratio estimated at 18 month visit will be reported along with 95% confidence interval.

8.6.2.4.3 Association of CDR Global Change at 18 Months with Tau Status

The association of change in CDR global score at 18 months by tau status (AD++ vs. non-AD++) will be assessed using a Cochran-Armitage trend test. The analysis will be performed with MCI/AD subjects. Frequency table, along with p-values for the trend test will be provided.

8.6.2.4.4 Diagnostic Performance of Baseline Tau Status in Predicting Clinical Meaningful Changes at 18 Months

This analyses will be restricted to AD/MCI subjects only.

For each cognitive assessment of cognitive impairment and TAU status, a 2x2 table will be generated and the appropriated diagnostic performance parameters determined.

CMC+ is defined as the clinically meaningful changes assessed by psychometric scores are defined in section 6.4.2.3.1. CMC- are those patient with related data but not meet the CMC+ definition.

		Clinical meaningful changes	
		CMC+	CMC-
AD++	A	B	
Non-AD++	C	D	

Sensitivity is defined as the number of Tau+ subjects who are cognitively impaired divided by the total number of subject with cognitive impairment.: $A/(A+C)$

Specificity is defined as the number of Tau- subjects who are not cognitively impaired divided by the total number of subjects without cognitive impairment. : $D/(B+D)$

Accuracy is defined as the number of subjects with cognitive impairment who are Tau+ and the number of subjects without cognitive impairment who are Tau- divided by the total number of patients. : $(A+D)/(A+B+C+D)$

Positive predictive Value is defined as the number of Tau+ subjects who are cognitively impaired divided by the total number of subjects who tested Tau+: $A/(A+B)$

Negative predictive value is defined as the number of Tau- subjects who are cognitively not impaired divided by the total number of subjects who test Tau-: $D/(C+D)$

Positive Likelihood Ratio (LR+) for positive result shows the odds of the cognitive impairment increases when TAU+: $Sensitivity/(1-Specificity)$

Negative Likelihood Ratio (LR-) for negative result shows the odds of the cognitive impairment decreases when TAU- : $(1-Sensitivity)/Specificity$

Relative risk: $(A/(A+B))/(C/(C+D))$

The analyses from 8.6.4.2.1 – 8.6.2.4.2, and 8.6.2.4.4 will be repeated with subjects with AD/MCI diagnosis and baseline MMSE 20 -27, which is similar to the target enrolled population in confirmatory cohort.

8.6.2.4.5 Multi-variate models to explore possible factors for cognitive impairments changes

The analysis will be completed for AB+ subjects. A multivariate step wise selection regression model will be used to explore factors associated with the change in psychometric score change at 18 months. The dependent variable will be each of these psychometric score change at 18 months respectively: ADAS Cog 11, MMSE, and FAQ. The independent variables include baseline information such as psychometric score (baseline ADAS Cog-11, MMSE, or FAQ), age, ANART score, APOE4 status (carrier or non-carrier), florbetapir SUVr, and flortaucipir MUBADA SUVr. The significance level of entry and stay in the model will be both set as 0.2. For each variable in the final model, the parameter estimate, SE, 95% CI and associated p-value will be reported.

Scatter plots will be generated for the following scenarios:

1. Change of ADAS score at 18 month versus Flortaucipir MUBADA SUVr score at baseline by each diagnostic groups.
2. Change of MMSE score at 18 month versus Flortaucipir MUBADA SUVr score at baseline by each diagnostic groups.
3. Change of FAQ score at 9 month or 18 month versus Flortaucipir SUVr score at baseline by each diagnostic groups.

8.7 Analysis of Safety

8.7.1 Extent of Exposure and Compliance to Study Treatment

The total dose administered (mCi) of Flortaucipir and florbetapir F 18 will be summarized using descriptive statistics (n, mean, SD, median, min, max, 25th, and 75th pct). Flortaucipir exposures will be summarized by each of the scans and all exposure data will be presented in listings.

Because this is a study with only one bolus of study medication per imaging visit, compliance will not be summarized.

8.7.2 Adverse Events

All AE summaries will be based on the set of TEAEs only. TEAEs will be summarized alphabetically by SOC and preferred term; a subject will only be counted once per SOC and once per preferred term. Subject counts and percentages will be presented for the following summaries:

1. All TEAEs by system organ class (SOC) and preferred term;
2. All TEAEs by preferred term (in order of descending frequency);
3. All TEAEs by relationship to study drug, SOC, and preferred term;
4. All TEAEs by relationship to protocol procedure, SOC and preferred term;
5. All TEAEs by severity, SOC and preferred term

For the summary of TEAEs by severity, if a subject has multiple events occurring in the same SOC or same preferred term, the event with the highest severity will be counted.

TEAEs by relationship to study drug and protocol procedure will be summarized as Related vs. Not Related. If a subject has multiple events occurring in the same SOC or same preferred term, the related event will be summarized.

Listings will be presented by subject for all TEAEs as well as for Serious TEAEs, TEAEs associated with death, and TEAEs associated with study discontinuation. Listings will also present adverse events relative to the first dose and relative to the Flortaucipir injection.

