7.7.2. Adverse Event Definitions

Adverse Events

For reporting purposes, Avid will distinguish among pre-existing conditions, treatment - emergent adverse events and trial-emergent adverse events. Pre-existing conditions (i.e., undesirable experiences, signs or symptoms that begin prior to the Screening Visit) will be recorded on the medical history and/or physical exam eCRF pages. Signs and symptoms that are believed to be due to the pre-existing condition (started prior to dose of study medication) do not have to be recorded in the AEs section of the eCRF, unless there is an increase in frequency or severity. Additionally, signs or symptoms or changes in pre-existing conditions that occur outside the trial defined adverse event reporting period (e.g., between the end of the baseline/cross-sectional imaging period and the 9 month follow-up imaging period) will be recorded in medical history.

An adverse event is any untoward medical occurrence associated with the use of a drug in humans, whether or not considered drug related. For the purposes of this study, untoward medical occurrences will be considered associated with the use of ¹⁸F-AV-1451, and thus be reported as adverse events, if they occur within 48 hours after ¹⁸F-AV-1451 administration, either at baseline or at the 9 or 18 month imaging visit. Untoward medical occurrences will be considered associated with the use of Florbetapir F 18 injection, if they occur within 48 hours after Florbetapir F 18 injection administration. Adverse events associated with the use of ¹⁸F-AV-1451 or Florbetapir F 18 injection will be recorded as treatment emergent relative to the respective drug. Adverse experiences that occur after administration of either drug but outside the 48 hour reporting window will not be reported unless the investigator believes they are attributable to the drug.

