In order to capture possible adverse effects of trial participation, trial-emergent adverse events will also be reported as any untoward medical occurrences occurring, during the baseline/cross-sectional imaging period but not during the 48 hour windows following the administration of ¹⁸F-AV-1451 or Florbetapir F 18 injection. For this purpose, the baseline/cross-sectional imaging period will be defined as beginning with the signing of consent and ending 48 hours after the last of the screening/baseline procedures described in sections [7.1.1 – 7.1.3](#), including (but not limited to) neuropsychological testing, MRI, ¹⁸F-AV-1451 or Florbetapir F 18 injection PET scanning and lumbar puncture.

The end of study for the purpose of adverse event reporting is defined as 48 hours after the last administration (i.e., 18 month visit or early termination visit) of ¹⁸F-AV-1451.

Serious Adverse Event (SAE)

An SAE is an AE that results in one of the following outcomes or constitutes one of the following events:

- Death;
- Initial or prolonged inpatient hospitalization (other than that required by protocol; “social hospitalization” or any hospitalization for non-medical reasons does not constitute an SAE);
- A life-threatening experience (that is, immediate risk of dying);
- Persistent or significant disability/incapacity;
- Congenital anomaly/birth defect;
- Considered significant by the investigator for any other reason.

Important medical events that may not result in death, be life-threatening, or require hospitalization may be considered serious adverse drug events when, based upon appropriate medical judgment, they may jeopardize the patient and may require medical or surgical intervention to prevent one of the outcomes listed in this definition.

Unexpected Adverse Event

An unexpected adverse event is an adverse event not previously reported or an adverse event that occurs with specificity, severity or frequency that is not consistent with the current investigator’s brochure.

Relationship to Investigational Product

Investigators will be instructed to report their assessment of the potential relatedness of each adverse event to protocol procedure, concomitant medication and/or investigational product. The assessment of the relationship of an adverse event to the administration of the investigational product is a clinical decision based on all available information at the time of the completion of the eCRF.

Intensity/Severity of an Adverse Event

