7.7.4. Reporting of Serious Adverse Events

Study site personnel must alert Eli Lilly or its designee of any SAE within 24 hours of their awareness of the event via a sponsor-approved method. Alerts issued via telephone are to be immediately followed with official notification on study-specific SAE forms.

Serious adverse events occurring after a subject receive a dose of investigational product will be collected until 48 hours after the dosing of the investigational product, regardless of the investigator's opinion of causation. Therefore, SAEs that occur later than 48 hours after the dosing of the investigational product are not required to be reported unless the investigator feels the events were related to either investigational product or a protocol procedure.

If a patient experiences an SAE after signing informed consent, but prior to receiving investigational product, the event will NOT be reported unless the investigator feels the event may have been caused by a protocol procedure. Previously planned (prior to signing the ICF) surgeries should not be reported as SAEs unless the underlying medical condition has worsened during the course of the study.

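### The SAP's adverse-event tables and its serious, death and discontinuation listings cover only events within 48 hours of a tracer injection, so other events that the protocol makes reportable are not tabulated

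*SAP*

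**What the plan says.** SAP 8.7.2 opens its adverse-event analysis with "All AE summaries will be based on the set of TEAEs only". It then names five tables, each of TEAEs, and listings of all TEAEs and of "Serious TEAEs, TEAEs associated with death, and TEAEs associated with study discontinuation". SAP 6.6.2 defines a TEAE by timing alone: onset or worsening between an injection of flortaucipir or florbetapir and 48 hours later. Investigator attribution plays no part in the definition.

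The protocol makes more than this reportable:

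- Section 7.7.2 creates a second class: "In order to capture possible adverse effects of trial participation, trial-emergent adverse events will also be reported". The period for this class is defined as "beginning with the signing of consent and ending 48 hours after the last of the screening/baseline procedures", with lumbar puncture (LP) among the procedures named, and it excludes the two 48-hour injection windows.
- Section 7.7.2 also says that post-dose events "outside the 48 hour reporting window will not be reported unless the investigator believes they are attributable to the drug", so late events attributed to the drug are reportable.
- Section 7.7.4 says that serious events later than 48 hours after dosing are "not required to be reported unless the investigator feels the events were related to either investigational product or a protocol procedure". For a serious event between consent and dosing, "the event will NOT be reported unless the investigator feels the event may have been caused by a protocol procedure".

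Protocol 8.2 commits to summarizing all subjects who have a serious adverse event (SAE) or who stop because of an adverse event. It sets no treatment-emergent limit. SAP 5.2, the section for departures from the protocol's analyses, mentions only the split into two phases.

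**The concern.** The protocol sets up the trial-emergent class to pick up harm from taking part in the study, and SAP 6.6.2 puts these events on the adverse-event page of the case report form. SAP section 8 then gives the class no table. For late or pre-dose serious events, the protocol admits exactly those that an investigator has linked to the product or a procedure. A safety reader would look for these first, yet they would be missing from the output labelled serious.

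The stake is whether the tabulated safety summary is complete. Expanding the flortaucipir safety database is a stated objective, though an exploratory one.

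**Working it through.** No figure in the plan needs recomputing. The check traces each reportable class of event through the SAP's definitions to its planned outputs.

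**Step 1: count the outputs in SAP 8.7.2.**

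| Output | Planned | Limited to TEAEs |
|---|---|---|
| Summary tables | 5 | 5 |
| Listings named by event type (all, serious, death, discontinuation) | 4 | 4 |
| Listing sentence with no stated limit (events relative to first dose and to flortaucipir) | 1 | 0 |

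The five tables break events down by organ class and preferred term, by preferred term alone, by relationship to drug, by relationship to procedure, and by severity.

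**Step 2: trace each class.**

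| Class reportable under the protocol | In a table? | In the serious listing, if serious? |
|---|---|---|
| Onset or worsening within 48 hours of injection | Yes | Yes |
| Trial-emergent (7.7.2) | No | No |
| After 48 hours, attributed to the drug (7.7.2) | No | No |
| SAE after 48 hours attributed to product or procedure, or SAE before dosing possibly caused by a procedure (7.7.4) | No | No |

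Each "no" has the same exception: an event that worsens inside a later 48-hour window becomes a TEAE and is counted.

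**Step 3: lumbar puncture.** SAP 6.4.3.4 says the LP should be at least 48 hours from the PET sessions. Let L be the time of the LP and I the time of an injection, in hours, so |L − I| ≥ 48.

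- If the injection came first, I + 48 ≤ L. The TEAE window has closed by the time of the LP.
- If the LP came first, I ≥ L + 48. The window opens only when the first 48 hours after the LP are over.

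The first 48 hours after an LP therefore overlap any TEAE window by 0 hours. An LP event that starts in that time cannot start as a TEAE. The table by relationship to procedure, the only one on procedures, misses it unless it worsens within 48 hours after a later injection.

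**Step 4: compare the two trial-emergent definitions.** Protocol 7.7.2 runs from consent to 48 hours after the last baseline procedure. SAP 6.6.2 covers only events before the imaging sessions or between the two of them. The LP is allowed within 60 days either side of the first flortaucipir scan, so it can follow both scans. As an illustration, take flortaucipir as the second scan on day 0, an LP on day 10 and a new event on day 11:

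- TEAE window: ended on day 0 + 2 = day 2, so the event is outside it.
- SAP trial-emergent class: the event is neither before nor between the scans, so it is outside.
- Protocol trial-emergent period: runs to at least day 10 + 2 = day 12, so the event is inside.

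The event is trial-emergent under the protocol and has no class under the SAP.

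**The case against.** The strongest reply is that little is lost, and several parts of it stand.

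- **General listings remain.** SAP 8.7.2 adds: "Listings will also present adverse events relative to the first dose and relative to the Flortaucipir injection". That sentence is not limited to TEAEs, and protocol 8.1 promises listings of all case-report-form data. A reader might infer that these events vanish from the report; the documents do not support that. What is missing is a count and, for the serious ones, a place in the serious listing.
- **Discontinuations are partly covered.** SAP 8.1 summarizes reasons for discontinuation, and SAP 8.3.1 bases disposition on the enrolled population. The undelivered part of protocol 8.2 is mainly the SAE summary.
- **The protocol itself restricts collection.** Its 48-hour reporting rules already exclude most unattributed late events, so the gap is confined to the classes traced above. Protocol 7.7.2 also sends events outside the reporting period to medical history. It is tempting to read the SAP 6.6.2 sentence that sends events during study visits to medical history as flatly contradicting protocol 7.7.3, which puts all adverse events on the adverse-event page. It is better read as a loose paraphrase of 7.7.2 that needs tidying.
- **Reporting is not tabulating.** Protocol 7.7.2 says that trial-emergent events will be reported, and protocol 8.1 leaves analysis detail to the SAP. The protocol 8.1 sentence on summarizing safety data for all patients most naturally concerns which subjects are included, so it is not relied on here. This reply does not answer the plain commitment in protocol 8.2 on subjects with SAEs.
- **Size is unknown.** A reader might want the share of LP events that would be missed. The number of LPs, their timing and the event rate are not given, and the SAP lists LP among the screening assessments, so most may precede the scans. No share of LP days, LPs or events is claimed.

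**Conclusion.** The point holds for tables and for the serious listing. All 5 tables and all 4 listings named by event type are limited to TEAEs, and no table admits trial-emergent or out-of-window attributed events unless they worsen inside a window. This is narrower than protocol 8.2 for SAEs and is not declared in SAP 5.2. The SAP's trial-emergent definition is also narrower than the protocol's, which can leave an event after a late LP unclassified.

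The conclusion assumes that SAP 8.7.2 is applied as worded and, for the LP argument, that the 48-hour spacing is kept. LP is optional, depends on site participation and is limited to subjects aged 50 or over. No efficacy result is affected. This is a cheap improvement to the safety reporting and does not threaten the study's conclusions.

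**What to change.** 1. In SAP 6.6.2, adopt the trial-emergent period of protocol 7.7.2: from consent to 48 hours after the last screening or baseline procedure, LP included, outside the TEAE windows. Reconcile the sentence on events during study visits with protocol 7.7.2 and 7.7.3.
2. In SAP 8.7.2, add one table of trial-emergent events and out-of-window attributed events, by organ class, preferred term and relationship to drug or procedure, with LP-related events identified. Base it on the enrolled population, because the safety population in SAP 8.3.2 requires an injection. This adds few subjects: those injected later are already in the safety population, and SAP 8.1 says that screening-failure data were not collected.
3. Make the serious, death and discontinuation listings, and an SAE summary, cover all recorded adverse events, each flagged as TEAE, trial-emergent or late-attributed.

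If the restriction to TEAEs is deliberate, record it with a reason in SAP 5.2.

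The cost is SAP wording, one extra table and longer listings. If sites followed the SAP's medical-history sentence for some events, the medical history form also needs a check.

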4 STUDY DESIGN

4.1 General Design

This study is an open label, multicenter Phase 2 study. This study is conducted in two phases, an exploratory (first) phase and complimentary (second) phase. The study will enroll cognitively healthy volunteers, subjects with mild cognitive impairment (MCI) and subjects with Alzheimer's disease. Approximately 230 subjects will be enrolled in the study: 80 cognitively healthy volunteers (20 subjects who will be ≥ 20 to ≤ 40 years of age, and 60 subjects who will be ≥ 50 years of age), 80 subjects with MCI, 70 subjects with AD (60 subjects with a Mini-Mental State Examination (MMSE) ≥ 20 , and 10 subjects with an MMSE > 10 and < 20). For the 60 cognitively healthy volunteers ≥ 50 years of age, these subjects will be distributed across age deciles (50-59, 60-69, 70-79 and > 80).

All subjects will provide informed consent before starting any study procedures.

Screening assessments may take place over several days and will include demographic information, cognitive testing, safety assessment, and MRI, including both volumetric and standard clinical sequences. Subjects who qualify for the study will undergo both a florbetapir F 18 PET imaging session and a Flortaucipir PET imaging session. The imaging sessions must be performed at least 48 hours apart, but not more than 60 days apart. The order of the scans is interchangeable. Some subjects, who are ≥ 50 years of age, will have the option to also participate in cerebrospinal fluid (CSF) collection by lumbar puncture (LP).

Subjects who are ≥ 50 years of age will return for have a follow-up visits at 9 (+/-2) months 18 (+/-2) following the initial Flortaucipir scan. Cognitive assessments and updates to concomitant medications and medical history will be collected at each follow-up visit. Subjects will also have follow-up Flortaucipir scans and MRI, including both volumetric and

standard clinical sequences. A sub-set of subjects may have the option to have an additional resting state functional (rsf) MRI sequence scan in addition to the volumetric and standard clinical sequences at both the screening MRI and follow-up MRIs. Subjects or their designated decision maker will be contacted by phone at 5 and 14 months following the initial Flortaucipir scan to collect updated concomitant medications and medical history.

Florbetapir F 18 PET Imaging Session:

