4.3 Method of Assignment of Subjects to Treatment Groups

Florbetapir F 18:

All subjects will receive a single IV bolus administration target dose of 370 MBq (10 mCi) of florbetapir F 18 injection.

Flortaucipir:

All subjects except for young cognitive normal (YCN) subjects will receive a single IV bolus administration target dose of 370 MBq (10 mCi) of Flortaucipir injection at each of the baseline, 9 months, and 18 months visits. YCN subjects will only receive a single IV bolus administration of Flortaucipir injection with a target dose of 370 MBQ (10 mCi) at baseline visit.

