All values will be summarized by the four diagnostic groups: young cognitively normal (YCN) subjects (healthy volunteers ≥ 20 years of age and ≤ 40 years of age), old cognitively normal (OCN) subjects (healthy volunteers ≥ 50 years of age), patients with AD, patients with MCI, and overall. Frequency distributions including counts and percentages will be included for all categorical outcomes. Summary statistics including mean, standard deviation, median, minimum and maximum values will be presented for all continuous outcomes. Unless otherwise specified, hypothesis testing will be two-sided with type I error rate of 0.05.

All statistical analyses will be performed using SAS® version 9.3 or higher.

7.2 **Adjustments for Covariates**

Not applicable for the primary analyses.

7.3 **Handling of Dropouts or Missing Data**

Dropout subjects will not be replaced in this study. For situations with no rules for handling missing data, the default will be no imputation.

A likelihood-based mixed effects model for repeated measures will be used to handle missing longitudinal follow up cognitive measurements, or flortaucipir SUVr data. The model parameters are simultaneously estimated using restricted likelihood estimation incorporating all of the observed data. Estimates have been shown to be unbiased when the missing data are missing at random and when there is ignorable non-random missing data.

Repeated measures analyses will only use data from visits where the data was scheduled to be collected. When subjects discontinue from the study early, there may be efficacy data measurements at visits where the variables were not scheduled to be collected. These data will appear in listings only.

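### Flortaucipir TEAEs are tabulated once per subject with no table by scan or per injection, so percentages for young controls (one injection) are not comparable with those of the other groups (up to three)

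*SAP*

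**What the plan says.** **Counting.** SAP 8.7.2 restricts the tables to treatment-emergent events ("All AE summaries will be based on the set of TEAEs only"). It chooses a per-subject metric ("Subject counts and percentages will be presented for the following summaries") and counts each subject once: "a subject will only be counted once per SOC and once per preferred term". It lists five summaries: by SOC and preferred term, by preferred term alone, by relationship to drug, by relationship to procedure, and by severity. None is by visit, scan or number of injections. Where a subject has several events within a term, the severity table keeps the worst one and the relationship tables keep the related one.

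**Grouping.** SAP 8.7.2 names no columns. They come from the general rule in SAP 7.1: "All values will be summarized by the four diagnostic groups", plus overall.

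**Exposure.** SAP 4.3 gives all other groups an injection "at each of the baseline, 9 months, and 18 months visits", whereas "YCN subjects will only receive a single IV bolus administration of Flortaucipir injection", at baseline. SAP 6.6.2 defines the flortaucipir TEAE window as the 48 hours after injection, and Protocol 7.7.2 applies that window at the baseline, 9-month and 18-month imaging visits. SAP 8.3.2 puts everyone who received flortaucipir into the safety denominator, whatever the number of injections.

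**Rest of the safety plan.** SAP 8.7.1 says that "Flortaucipir exposures will be summarized by each of the scans". Laboratory, vital-sign and ECG data are summarised by time point (SAP 8.7.3, 8.7.4.1, 8.7.4.2). SAP 8.7.2 also plans subject listings that place events relative to the first dose and to the flortaucipir injection.

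**The concern.** A percentage of subjects with at least one event depends on how long, or how often, each subject was at risk. Here the number of at-risk windows is fixed by design at one for YCN and up to three for everyone else, but all sit over the same per-subject denominator. With the same risk at every injection, YCN would still show fewer affected subjects. The worst-severity and any-related rules push in the same direction, because they pick from up to three windows outside YCN and from one within it.

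The second consequence concerns repeat injections. Expanding the safety database is an objective of the longitudinal component (SAP 3.2) as well as of the cross-sectional one (SAP 3.1), and the second and third injections occur only in the longitudinal component. A table collapsed over sessions does not show whether TEAEs become more or less common as injections accumulate.

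**Working it through.** The documents give no adverse-event rate or safety precision figure, so there is nothing to reproduce first. The per-injection TEAE risk *p* is an assumption, shown from 1% to 20%.

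**1. Planned exposure.** Cognitively healthy group sizes (SAP 4.1): "20 subjects who will be ≥ 20 to ≤ 40 years of age, and 60 subjects who will be ≥ 50 years of age". The same section plans 80 MCI and 70 AD.
- YCN: 20 × 1 = 20 injections.
- Others: (60 + 80 + 70) × 3 = 210 × 3 = 630 injections.
- Total: 650 injections in 230 subjects, an average of 650/230 = 2.83 windows per subject. The overall column therefore describes neither one injection nor three.

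**2. Subject-level incidence at equal per-injection risk.** With *k* independent windows, P(at least one event) = 1 − (1 − p)^k. At p = 5%: YCN 5.0%; three injections 1 − 0.95³ = 14.3%; ratio 2.85.

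**3. Two sensitivity checks.**
- Dropout: assume 10% receive one injection only, 10% two and 80% three. The 20% total is borrowed from the confirmatory-phase assumption in Protocol 8.1.1.2; the even split is assumed. At p = 5%: 0.10 × 5.0% + 0.10 × 9.75% + 0.80 × 14.26% = 12.9%, ratio 2.58.
- Within-subject correlation ρ (beta-binomial, all three injections given): set a = p(1 − ρ)/ρ and b = (1 − p)(1 − ρ)/ρ. Then P(no event in three) = [b/(a+b)] × [(b+1)/(a+b+1)] × [(b+2)/(a+b+2)]. At p = 5%, ρ = 0.5: 0.95 × 0.975 × 0.9833 = 0.911, so incidence is 8.9% and the ratio 1.78.

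| p per injection | One injection (YCN) | Three injections | Ratio, independent | Ratio, 20% dropout | Ratio, ρ = 0.1 | Ratio, ρ = 0.5 | Ratio, ρ = 0.9 |
|---|---|---|---|---|---|---|---|
| 1% | 1.0% | 3.0% | 2.97 | 2.68 | 2.69 | 1.82 | 1.15 |
| 2% | 2.0% | 5.9% | 2.94 | 2.65 | 2.67 | 1.81 | 1.15 |
| 5% | 5.0% | 14.3% | 2.85 | 2.58 | 2.60 | 1.78 | 1.14 |
| 10% | 10.0% | 27.1% | 2.71 | 2.46 | 2.48 | 1.73 | 1.14 |
| 20% | 20.0% | 48.8% | 2.44 | 2.23 | 2.26 | 1.64 | 1.12 |

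The ratio exceeds 1 throughout. Its size runs from about 1.1 to 3.0.

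**4. Pattern over injections.** Suppose the risk rises over the three sessions as 2%, 4%, 8%. Cumulative incidence is 1 − 0.98 × 0.96 × 0.92 = 13.45%. If it falls as 8%, 4%, 2%, the product is the same, so incidence is again 13.45%. The planned tables would not separate the two.

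**5. With tables by session.** At equal per-injection risk each session's expected percentage is *p* in every group, so the ratio at baseline is 1.0. The two patterns in step 4 would appear as different rows.

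**The case against.** The case on the other side is substantial, and much of it stands.

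- **Counting subjects once is ordinary practice and follows the protocol.** Protocol 8.2 asks for the number and percentage of subjects with an AE. That stands: the pooled table belongs in the report. The gap is that it is the only display when exposure differs up to threefold by design.
- **SAP 8.7.2 states neither the grouping nor pooling over sessions.** True. The grouping is taken from SAP 7.1, and pooling is the natural reading of five summaries with no session dimension.
- **No between-group test of AEs is planned, and YCN is small.** Also true. At p = 5% the expected number of affected YCN subjects is 20 × 0.05 = 1, and the chance of seeing none is 0.95^20 = 36%. SAP 8.6.1.1 already leaves YCN out of the main imaging ANOVA because of age. The result would be a misleading description, not a false statistical conclusion.
- **A reader might infer that repeat-injection safety cannot be learned from the planned output.** The documents do not support that. Listings place events relative to dosing, exposure is given by scan, and laboratory, vital-sign and ECG data are given by time point. Only the TEAE summary tables lack the session dimension.
- **A reader might also infer that all diagnostic groups are distorted against each other, or that results clash with the confirmatory cohort.** Neither follows. OCN, MCI and AD share the same planned exposure and would differ only if dropout differed, and no dropout figure by group is given. The phases have separate subjects and analyses (Protocol 2), and no AE comparison between them is planned.

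**Conclusion.** The point holds within limits. As planned, YCN percentages and the overall column of the flortaucipir TEAE tables are not comparable with those for OCN, MCI and AD, because YCN contribute one window and the others up to three. At equal per-injection risk the other groups would show roughly 1.1 to 3.0 times the YCN rate. The figure of about 2.7 to 2.9 applies only to risks of 2% to 10% with independent windows and no dropout, so it should not be read as a firm threefold effect. Both the risk and the correlation are assumptions. Any trend over repeat injections is missing from the summary tables, though recoverable by hand from the listings. No planned estimate or test depends on this, so it is a cheap improvement in reporting and does not threaten the study's conclusions.

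**What to change.** In SAP 8.7.2:

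- Add flortaucipir TEAE summaries by imaging session (baseline, 9 months, 18 months), with the subjects injected at that session as denominator.
- Add one overall line giving TEAEs per injection.
- State that YCN are set beside the other groups on the baseline session only.
- Keep the pooled per-subject table that Protocol 8.2 asks for, and say in 8.7.2 that it covers all sessions and uses the SAP 7.1 columns.

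The cost is SAP wording and a few extra tables with sparser cells. No new data are needed, because the planned listings already require event timing relative to dosing. The 9- and 18-month tables will describe only subjects who returned for those scans, which a footnote can say.
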